2 STUDY OBJECTIVES

2.1 Primary

To investigate the safety and tolerability of daily oral administration of SPH3127 given as one 50 mg tablet in the morning and one placebo tablet in the evening, or given as one 50 mg tablet in the morning and one 50 mg tablet in the evening (100 mg total daily dose) or placebo (one placebo tablet in the morning and evening) for 8 weeks in patients with mild-to-moderate ulcerative colitis.

2.2 Secondary

To investigate the pharmacokinetics and pharmacodynamics of daily oral administration of SPH3127 (50 or 100 mg total daily dose) or placebo for 8 weeks in patients with mild-to-moderate ulcerative colitis.

3 STUDY ENDPOINTS

In this exploratory study, a variety of safety endpoints will be evaluated, including, but not limited to:

1. Vital signs (systolic and diastolic blood pressure (seated) and pulse/heart rate, temperature);

- 2. Physical examination;
- 3. Clinical laboratory tests (hematology, serum chemistry, urinalysis); and,
- 4. Adverse events.

In this exploratory study, a variety of efficacy and translational endpoints will be evaluated, including, but not limited to:

- 5. Proportion of patients in clinical remission at week 8;
- 6. Endoscopic improvement (MCES subscore ≤1) at week 8;
- 7. Endoscopic remission (Mayo Clinic Endoscopic Subscore (MCES) subscore of 0) at week 8;
- 8. Endoscopic response (>1-point reduction in MCES) at week 8;
- 9. Symptomatic remission at week 8;
- 10. Reduction in rectal bleeding subscore of 0 at week 8;
- 11. UC-100 score improvement at week 8;
- 12. Improvement in clinical response at week 8;
- 13. Change in fecal calprotectin concentration at week 8;
- 14. Improvement in Robarts Histology Index;
- 15. Change in tissue biomarkers (e.g., angiotensin II, complement C3, IL-1β, IL-17A, TNF-α, IL-6, and IL-23);
- 16. Change in plasma and tissue PK; and,
- 17. Correlation of change in tissue biomarkers with endoscopic and histology response.

4 STUDY PLAN

4.1 Study Design

In this double-blind, placebo-controlled, multi-center trial, patients ≥ 18 to ≤ 70 years of age with mild-to-moderate ulcerative colitis (UC) will be randomly assigned to daily oral treatment with SPH3127 (given as one 50 mg tablet in the morning and one placebo tablet in the evening, or given as one 50 mg tablet in the morning and one 50 mg tablet in the evening (100 mg total daily dose) or matching placebo tablets (one placebo tablet in the morning and evening) for 8 weeks. The objective of this study is to assess the safety and tolerability of SPH3127. In addition, the PK and PD effects of SPH3127 will be

assessed; PD effects will be assessed through plasma and colitis lesion biomarkers and validated measures of disease activity (e.g., modified Mayo Score (MMS), UC-100, Robarts Histology Index (RHI) and fecal calprotectin).

A total of 30 eligible patients will be randomly assigned to one of three treatment arms (10 subjects per treatment group):

- Treatment A: 50 mg SPH3127 (given as one 50 mg tablet in the morning and one placebo tablet in the evening) PO daily for 8 weeks
- Treatment B: 100 mg SPH3127 (given as one 50 mg tablet in the morning and one 50 mg tablet in the evening) PO daily for 8 weeks
- Treatment C: Matching placebo tablets PO daily (given as one tablet in the morning and one tablet in the evening) for 8 weeks

A patient will be considered enrolled in the trial once they have provided signed informed consent, met all inclusion/exclusion criteria, been randomized to treatment and received at least one dose of study drug. Baseline measurements will be taken at screening or on Day 1 prior to the first treatment.

After the 12-week trial period (including screening), all randomized subjects will have the opportunity to enter an optional active treatment extension for an additional 10 months. Those subjects receiving Treatment A and who choose to enter the extension will continue on Treatment A in a blinded manner (will not know SPH3127 dose). Those subjects receiving Treatment B and who choose to enter the extension will continue on Treatment B in a blinded manner (will not know SPH3127 dose). Those subjects receiving Treatment C (placebo) and who choose to enter the extension will be randomized to receive Treatment A or Treatment B in a blinded manner (will not know SPH3127 dose). Those subjects who choose not to enter the optional active treatment extension will receive a follow-up safety call one week after the last treatment (D63). The STUDY SCHEMATIC is presented in Figure 1.

4.2 Schedule of Assessments

	Main Study								Active Treatment Extension					
Event	D-28 ± 2	D-5 ± 2	D1	D14 ± 2	D28 ± 2	D46 ± 2	D56 ± 2	$D63^d \pm 4$	D112 ± 4	D168 ± 4	D224 ± 4	D280 ± 4	D336 ± 4	
Informed Consent	X													
Screening	X													
Medical History/ Demographics	X													
Physical exam	X		X	X	X		X						X	
Vital Signs (BP, HR, Temp)	X		X	X	X		X		X	X	X	X	X	
ECG	X		X				X							
Stool sample ^e	X													
Labs	X		X	X	X		X		X	X	X	X	X	
Urine drug screen, alcohol breathalyzer	X													
Urine pregnancy test	X		X											
Con Meds	X		X	X	X		X		X	X	X	X	X	
AEs	X		X	X	X		X	X	X	X	X	X	X	

		Main Study								Active Treatment Extension					
Event	D-28 ± 2	D-5 ± 2	D1	D14 ± 2	D28 ± 2	D46 ± 2	D56 ± 2	D63 ^d ± 4	D112 ± 4	D168 ± 4	D224 ± 4	D280 ± 4	D336 ± 4		
Modified Mayo Clinical Score															
Stool Frequency ^a	X		X	X	X		X		X	X	X	X	X		
Rectal Bleeding ^a	X		X	X	X		X		X	X	X	X	X		
Flexible Sigmoidoscopy ^b	X						X						X		
UC-100 Score	X						X						X		
UC Lesion Samples ^c															
Robarts Histopathology Index ^b	X						X						X		
Biomarkers	X						X								
I/E Confirmation (phone call to patient)		X													
Plasma Biomarkers (-10", 1', 2', 4', 8')			X		X		X								
PK (-10", 15", 30", 1', 2', 4', 8')			X		X		X								
Fecal Calprotectin	Xe				X		X								

		Main Study							Active Treatment Extension				
Event	D-28 ± 2	D-5 ± 2	D1	D14 ± 2	D28 ± 2	D46 ± 2	D56 ± 2	$D63^{d} \pm 4$	D112 ± 4	D168 ± 4	D224 ± 4	D280 ± 4	D336 ± 4
Dispense Medication and Perform Accountability			X	X	X		X		X	X	X	X	
Take Medication on Site			X	X	X		X						
Participation in extension? (phone call to patient)													
Post-Study Follow-Up ^d								X					

^aVia patient report at D-28. Via electronic diary starting at D-5.

^bWithin 2 weeks after D-28 (screening) and within 2 days after D56 and D336

^cSamples collected during sigmoidoscopy

^dPatients who don't enter the active treatment extension will receive a post-study phone call to query for adverse events.

^eWithin 2 weeks after D-28 (screening). If possible, the first stool of the day should be collected. Sample should not be collected on the day of sigmoidoscopy or bowel preparation.

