6.2.6 Day 63 (\pm 2 days) Follow-Up (phone)

• Query for adverse events (phone call only for subjects not entering the active treatment extension)

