6.2.7 Active Treatment Extension

All randomized subjects will have the opportunity to enter an active treatment extension after the last main study visit (Day 56). A phone call will be made to each subject to confirm interest in participating on Day 46 ± 2 . Medication will be dispensed at 8-week intervals in the same 2-week blister packs as the main study for an additional 10 months in the active treatment extension. Those subjects receiving Treatment A (50 mg SPH3127 total daily dose) and who choose to enter the extension will continue on Treatment A in a blinded manner (will not know SPH3127 dose). Those subjects receiving Treatment B (100 mg SPH3127 total daily dose) and who choose to enter the extension will continue on Treatment B in a blinded manner (will not know SPH3127 dose). Those subjects receiving Treatment C (placebo) and who choose to enter the extension will be randomized to receive Treatment A or Treatment B in a blinded manner (will not know SPH3127 dose). Safety information (i.e., adverse events, clinical laboratory tests, vital signs, concomitant medications) will be collected at the designated intervals (every 8weeks) in the Schedule of Assessments. Rectal bleeding and stool frequency will be collected daily using a subject diary. At the final site visit (D336), a physical examination and flexible sigmoidoscopy (within 2 days of visit) will also be performed.

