6.3 Premature Discontinuation

An enrolled subject is defined as having signed an informed consent, met all inclusion/exclusion criteria, been randomized to treatment and having received at least one dose of study drug.

A subject has the right to withdraw from the study at any time for any reason without prejudice or without jeopardizing their medical care. The Investigator must withdraw the subject from the study if the subject requests to be withdrawn.

The Investigator may discontinue a subject from the study when, in his/her judgment it is necessary for any reason, including any of the following:

- Adverse event (serious or non-serious);
- Failure to comply with the protocol;
- Requires a medication that is specifically prohibited by the protocol; or,
- It is in the subject's best interest.

The Investigator may also withdraw a subject upon the request of the Sponsor, or if the Sponsor terminates the study for clinical or administrative reasons.

If a subject is withdrawn from participation in the study, the reason(s) for discontinuation shall be documented. A subject who discontinues the study early (regardless of cause) will be requested to return to the clinic and have all the early termination assessments

performed. If a subject is discontinued from study due to an adverse event, the subject will be followed until the event is resolved or deemed clinically stable.

A subject that has been met all the eligibility criteria at Screening, but not at baseline (Day 1), will be replaced. A subject that has enrolled in the study (signed informed consent, met all inclusion/exclusion criteria, has been randomized and received at least one dose of study drug) that discontinues from the study (for any reason) will not be replaced.

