8 STUDY DRUG MANAGEMENT

8.1 Description

8.1.1 Formulation

SPH3127 50 mg tablets or matching placebo tablets will be packed in blister cards (PVC with foil back) containing a 2-week supply (one tablet per day) plus 2 extra tablets to account for Visit scheduling (i.e., 2 x 8 configuration). Each blister card is packed individually in a foil pouch. Subjects will receive 2 blister cards (in foil pouches) for each 2-week period and will take one tablet orally from each blister card daily.

The study drug products (SPH3127 and placebo tablets) will be packaged with the following labeling information:

- serial number (for blinding and randomization)
- protocol number
- Sponsor's identification
- investigational new drug statement
- drug product name and potency
- drug product manufacturer
- route of administration
- instructions for use and storage
- precautionary statements

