8.6 Compliance

Patients will be asked to return their blister card(s) at each post-randomization study visit (except Day 1).

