9.1 Documenting Adverse Events

The recording of AEs (regardless of their relationship to study drug) will begin with the Screening Visit until the Final Visit (Day 56) or Early Termination Visit. If the Investigator is made aware of an AE up to 7 days after the last dose of study drug the AE will be followed to resolution. For those patients who enter the optional active treatment extension, Investigator(s) will query patients for AEs when they visit the site to pick up their medication every 8 weeks. Investigator(s) will monitor each patient closely for AEs. At each visit, the Investigator will document all observed or volunteered AEs.

The Investigator(s) should always attempt to group signs and symptoms into a single term that constitutes a single unifying diagnosis. Adverse Events will be classified using the latest version of the Medical Dictionary for Regulatory Activities (MedDRA) classification system. AEs reported from the first dose of IP until 7 days after the last dose of IP will be considered as treatment-emergent AEs (TEAEs) and will be summarized descriptively. The Investigator's opinion of the association of each AE to study drug, the duration (date of onset / date of resolution), frequency, intensity, countermeasures (treatment), and the outcome of each AE will be documented. Each adverse event must be recorded separately. Multiple occurrences of a single PT in a patient will only be counted once at the maximum severity/grade. All AEs will be summarized by relatedness to IP. Any AEs leading to death or discontinuation of IP will also be summarized.

Any medical condition or laboratory abnormality that is present at subject screening and prior to the first dose of study drug should be considered as baseline, recorded in medical history, and should not be reported as an AE. However, if the medical condition worsens at any time during the study after the first dose of study drug it should be recorded as an adverse event.

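### Extension patients have no scheduled adverse-event query after their last visit, although treatment-emergent events count for 7 more days and patients leaving at Day 56 do get a one-week call

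*Combined protocol and SAP*

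**What the plan says.** **Who is called.** The Study Summary, 4.1, footnote d of 4.2 and 6.2.6 all give the post-dosing call only to patients who leave at the end of the main study. Under footnote d, these patients "will receive a post-study phone call to query for adverse events". Section 6.2.6 reads: "Query for adverse events (phone call only for subjects not entering the active treatment extension". The Summary and 4.1 time the call one week after last dose (D63). The window is ±4 days in 4.2 and ±2 days in 6.2.6.

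**Extension patients.** The AE row in 4.2 ends at D336, the last column. Section 9.1 adds no later query: "Investigator(s) will query patients for AEs when they visit the site to pick up their medication every 8 weeks". The last dispensing mark is D280. For early stoppers, 6.3 says: "A subject who discontinues the study early (regardless of cause) will be requested to return to the clinic". It asks for early termination assessments there and schedules no call afterwards.

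**What runs past the last query.** Section 9.1 states: "AEs reported from the first dose of IP until 7 days after the last dose of IP will be considered as treatment-emergent AEs". Section 9.4 acts on suspected pregnancies over the same 7 days. At the D336 visit, 6.2.7 says that "a physical examination and flexible sigmoidoscopy (within 2 days of visit) will also be performed". Footnote b places the sigmoidoscopy within 2 days after D336, and the histology index is marked there, so tissue is taken.

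**Where recording ends.** Section 9.8 stops SAE recording at the final visit (Day 56, or Day 336 for extension patients) or at early termination. Section 10.3 ends monitoring at Day 63 for the main study, or with the extension period.

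**The concern.** Safety and tolerability are the primary objective (2.1), and extension visits mainly collect safety data (6.2.7). Under 9.1 the plan counts a week after last dose as treatment-emergent, but for extension patients it schedules no question about that week. Patients treated for 8 weeks are called a week later; those treated for up to about 48 weeks are not, and no reason is given. Late AEs, and delayed events after the final biopsied examination, would then reach the database only if the patient volunteers them or staff happen to see them.

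**Working it through.** **1. The plan's own figure.** Last dose at Day 56 plus 7 days: 56 + 7 = 63. This reproduces the D63 call.

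**2. Same rule for the extension.** 336 + 7 = D343. With the ±4-day visit window and the last dose on the visit day, the call would fall on D339 to D347. The schedule has nothing there.

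**3. Days of the 7-day window reached by the D336 query.** Let V be the visit day and L the last-dose day. Days reached = min(7, V − L).

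| Last dose | Days reached at the visit | If the sigmoidoscopy, 0 to 2 days later, is counted as an informal contact |
|---|---|---|
| On the visit day | 0 of 7 | 0 to 2 of 7 |
| The day before | 1 of 7 | 1 to 3 of 7 |
| 7 or more days before | 7 of 7 | 7 of 7 |

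**4. Does drug supply force an early stop?** Section 8.1.1 gives each card a "2-week supply (one tablet per day) plus 2 extra tablets to account for Visit scheduling", which is 14 + 2 = 16 tablets. Two cards cover each 2-week period, with one tablet a day from each.

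- D280 dispensing covers 8 weeks: 4 periods × 16 = 64 days.
- Shortest interval from D280 to D336: 332 − 284 = 48 days. Longest: 340 − 276 = 64 days.
- If the new supply starts on the D280 visit day, its last day is day 63 after that visit. In the longest interval this is 64 − 63 = 1 day before the D336 visit.

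Supply therefore allows dosing up to the visit or the day before, on any permitted timing. This does not show when patients actually stop. Dosing after the visit is unlikely, because 8.6 says: "Patients will be asked to return their blister card(s) at each post-randomization study visit (except Day 1".

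**5. Final sigmoidoscopy.** Latest day: 336 + 4 + 2 = D342. With the last dose on the visit day and the procedure 2 days later, 7 − 2 = 5 days of the window remain after it.

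**6. The Day 63 call.** Take the last dose on the Day 56 visit, D54 to D58.

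- Calendar reading, ±4: call on D59 to D67, so 59 − 58 = 1 to 67 − 54 = 13 days after last dose.
- Calendar reading, ±2: call on D61 to D65, so 61 − 58 = 3 to 65 − 54 = 11 days.
- Timed from last dose, as in the Summary and 4.1: 7 ± 4 = 3 to 11 days, or 7 ± 2 = 5 to 9 days.

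On every reading the call can come before the 7-day period ends.

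**The case against.** **There are two definitions of treatment-emergent.** Section 10.3.1 counts events with onset during the treatment phase, or worsening of a preexisting condition, and gives no 7-day tail. On that wording the uncovered week might not count. The 9.1 rule also classifies events that are reported; it does not promise to ask. This stands as an inconsistency to settle. It does not remove the point, because 9.1 is explicit and the one-week call for leavers follows the same logic.

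**Other provisions exist.** Section 9.1 follows an event that the investigator learns of within 7 days of last dose, and 9.5 allows up to 7 days of follow-up. Section 6.3 follows patients withdrawn for an AE until it resolves or is stable, and 9.3 repeats clinically significant abnormal laboratory tests. These protect patients with known events. None schedules a question that would find a new one.

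**The yield is small.** Plasma half-life is 3 to 6 hours (1.3.2), so 7 days (168 hours) is 168/6 = 28 to 168/3 = 56 half-lives. Section 1.3.3 says that the effect on renin outlasts plasma levels. Extension AEs are queried at five visits over 336 − 56 = 280 days, and 7/280 = 2.5%. This largely stands and limits the weight of the point.

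**Timing is uncertain.** The last-dose day is not stated. Section 6.2.7 places the sigmoidoscopy within 2 days of the visit, which need not mean after it; only footnote b says after. D342 is a worst case.

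**Stronger readings that the documents do not support.** A reader might infer that 9.8 singles out extension patients. It does not: it ends SAE recording at the final visit for both groups. A reader might also infer that the missing call leaves pregnancies uncovered in extension patients only. The existing call asks about AEs alone, and 9.4 is triggered by suspicion from any source, so extending that call unchanged would not close the pregnancy window.

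**Conclusion.** The point holds as a gap in active ascertainment. No AE query is scheduled for extension patients after D336 or early termination, while 9.1 counts 7 further days. For a last dose on the visit day or the day before, the visit reaches 0 or 1 of those days. Coverage is complete only if dosing stopped at least 7 days earlier. These figures rest on the 9.1 definition and on an assumed last-dose day.

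A reader might infer that a treatment comparison is biased. The documents do not support that: everyone in the extension is on active drug, both dose groups follow the same schedule, and the number of missed events cannot be estimated. At most 30 patients are affected and few events are likely to be missed. This is a cheap improvement to primary-objective data.

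**What to change.** - Give every extension patient, including early stoppers, one phone call 7 days (+4/-0) after last dose and after any final sigmoidoscopy. If dosing stopped well before that procedure, the later condition governs. Ask about AEs and suspected pregnancy.
- Add a column after D336 in 4.2 and amend footnote d, the Summary, 4.1, 6.2.6, 6.2.7 and 6.3 to match. With the last dose on the visit day, the call falls between 332 + 7 = D339 and 340 + 11 = D351, which is 7 − 2 = 5 to 11 − 0 = 11 days after the sigmoidoscopy.
- Run AE and SAE recording through the follow-up call for both groups in 9.1, 9.5, 9.8 and 10.3.
- Align the 10.3.1 definition with the 7-day rule in 9.1.
- Use one window for the Day 63 call in 4.2 and 6.2.6, opening no earlier than day 7 after last dose. The same +4/-0 would serve.

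**Cost.** At most 30 calls, or 30/20 = 1.5 per site over about 20 sites, with recording extended 7 to 11 days past last dose. The amendment needs IRB approval before use (11.2, 14) and may require a revised consent form. No visit or procedure is added.

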5 POPULATION

5.1 Number of Subjects

30 mild-to-moderate ulcerative colitis patients

5.2 Number of Study Sites

 \sim 20 sites in the U.S.

5.3 Inclusion Criteria

- 1. Signed Informed Consent Form (ICF);
- 2. Adult males and females \geq 18 to \leq 70 years of age on the day of signing the ICF.
- 3. A diagnosis of UC (documented or confirmed at screening) will be eligible provided they have mild-to-moderate active UC extending ≥ 15 cm from the anal verge.
- 4. At screening/baseline, a Modified Mayo Clinic Score (MMCS) from 4-9, a rectal bleeding subscore ≥ 1, and a Mayo Clinic Endoscopic Subscale (MCES) score ≥ 2 determined by central reading.
- 5. Patient has a negative urine drug screen (e.g., amphetamines, barbiturates, benzodiazepines, cannabis, cocaine, opiates, methadone) at Screening.
- 6. Patient has a negative alcohol breath test at Screening.
- 7. Female patients who have a negative pregnancy test at Screening and who agree to use adequate birth control methods throughout the entire study (and extension, if applicable) or who is post-menopausal (i.e., amenorrhea ≥ 1 year) or who have been surgically sterilized.
- 8. Male patients with partners of child-bearing potential who agree to use adequate birth control methods throughout the entire study (and extension, if applicable) or who have been surgically sterilized.

5.4 Exclusion Criteria

An eligible subject will not be enrolled in the trial if any of the following exclusion criteria are met:

- 1. Diagnosis of severe UC, defined as the presence of ≥ 6 bloody stools daily with one or more of the following: (1) oral temperature > 37.8°C or > 100.0°F; (2) pulse > 90 beats/min; (3) hemoglobin concentration < 10.5 g/dL; or erythrocyte sedimentation ratio (ESR) > 30.
- 2. Patients treated with oral mesalamine >2.4 g/d, systemic steroids or rectal steroids within 4 weeks prior to randomization, rectal mesalamine (within 2 weeks), immunomodulators or immunosuppressant drugs, including, but not limited to, IL-6 inhibitors, TNF inhibitors, anti-IL-1 agents and JAK inhibitors within 5 half-lives prior to randomization, antibiotics, anti-diarrheals (within 2 weeks), drugs blocking the renin-angiotensin system (e.g., direct renin inhibitors, angiotensin converting enzyme inhibitors, or angiotensin II receptor blockers) (within 4 weeks) or

administration of any investigational drug (within 4 weeks). Because SPH3127 is a direct renin inhibitor with the potential to reduce blood pressure, other classes of antihypertensives (e.g., calcium channel blockers, beta blockers, direct vasodilators, alpha blockers, central α2 antagonists) (within 4 weeks) will also be excluded. Drugs, herbal medicines and substances that inhibit or induce CYP3A4 (e.g., ritonavir, itraconazole, grapefruit juice) (within 2 weeks or 5 half-lives, whichever is longer) will be excluded.

- 3. History of colectomy or partial colectomy, colorectal dysplasia, Crohn's disease, toxic megacolon, or bleeding disorders.
- 4. A stool sample positive for enteric pathogens, including *Clostridium difficile*.
- 5. Patients with an estimated glomerular filtration rate (eGFR) \leq 60.
- 6. Patients with hepatic impairment or history of liver cirrhosis.
- 7. Serum creatinine > 1.5 times the upper limit of normal, aspartate aminotransferase (AST), alanine aminotransferase (ALT), total bilirubin (TBIL) or alkaline phosphatase (ALP) > 2 times the upper limit of normal.
- 8. Serious underlying disease other than UC.
- 9. Previous participation in clinical trials with SPH3127
- 10. Known hypersensitivity to tablet ingredients or history of a significant allergic reaction to any drug as determined by the investigator.
- 11. Known seropositivity or positive test at screening for an active viral/bacterial infection with:
 - Hepatitis B virus (HBV) (except seropositivity due to HBV vaccination)
 - Hepatitis C virus
 - Human immunodeficiency virus
 - COVID-19 (only active infection excluded)
 - Tuberculosis
- 12. Known clinically relevant immunological disorders.
- 13. History of severe allergic or anaphylactic reactions.
- 14. History of malignancy, unless deemed cured by adequate treatment with no evidence of recurrence for a minimum 3 years before screening; completely eradicated non-melanoma skin cancer (such as basal cell carcinoma or squamous cell carcinoma) is not exclusionary.
- 15. Clinically relevant abnormalities detected on ECG regarding either rhythm or conduction (e.g., QTcF > 450 ms or a known long QT syndrome). A first-degree heart block or sinus arrhythmia will not be considered a significant abnormality.
- 16. Low blood pressure at screening (i.e., SBP < 90 mmHg or DBP < 60 mmHg).
- 17. Clinically relevant abnormalities detected on vital signs prior to dosing.

- 18. Significant blood loss (including blood donation > 500 mL) or transfusion of any blood product within 12 weeks prior to the IP administration or scheduled transfusion within 4 weeks after the end of the trial
- 19. Treatment with any drug known to have a well-defined potential for toxicity to a major organ in the last 3 months preceding the initial investigational product (IP) administration
- 20. Concurrent participation, or participation within 30 days prior to the IP administration or 5 half-lives of the investigational drug (whichever is longer), in any drug/device or biologic investigational research trial.
- 21. Women who are breastfeeding.
- 22. Vaccination (including influenza and COVID-19) within the last 4 weeks prior to randomization.
- 23. History of drug or alcohol abuse.
- 24. Is an investigator, sub-investigator, research assistant, pharmacist, trial coordinator, or other staff of a relative who is directly involved in the conduct of the trial.
- 25. Any condition or circumstances that in the opinion of the investigator may make a subject unlikely or unable to complete the trial or comply with trial procedures and requirements.

